Intervention: The Coach2Move approach is stepwise implemented in 16 physiotherapy practices. On each site, at least one physiotherapist in geriatrics and one physiotherapist will receive a two-day training in the Coach2Move approach, which makes use of elements of the Hypothesis Oriented Approach for Clinicians (HOAC-II) and the International Classification of Functioning and Health (ICF). Participants receive physiotherapy according to the Coach2Move approach instead of the usual care physiotherapy.

Main study parameters/endpoints: In this study, each participant is measured four times. The first, being the baseline measurement (T0) is prior to physiotherapeutic treatment, while the second is directly after ending the treatment (T1). The following two are respectively six- (T2) and twelve months (T3) after the moment the participant started the treatment.

The primary outcome measures are the cost per quality-adjusted life year (QALY) gained, mobility measured by the modified Timed up and Go (TUG) and the level of moderate physical activity (LAPAQ). Secondary outcomes include: quality of life (EQ-5D), the degree of frailty (Evaluative Frailty Index for Physical activity), perceived effect (Global Perceived Effect and Patient Specific Complaints) and health care utilization costs.

In addition, qualitative data of experiences in implementation of Coach2Move will be gathered from interviews with patients and focus groups with PTG's and PTs.

The quantitative analysis will be based on quality indicators of medical records of patients for each physiotherapist scored by the researcher. The files in the control period are compared with those after implementation of Coach2Move.

Nature and extent of the burden and risks associated with participation, benefit and group relatedness: The physiotherapeutic process according to the Coach2Move strategy does not have more risk compared to usual care physiotherapy. The additional load related to the study participants are being exposed to consists of the three measurement moments in which questionnaires are being conducted. These moments each will take the patients approximately 60 minutes.

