A new and promising approach to help frail older adults to increase their levels of physical activity is Coach2Move. This strategy, based on clinical reasoning conform the Hypothesis Oriented Algorithm for Clinicians (HOAC-II) and the International Classification of Health (ICF), provides guidance in the diagnostic and therapeutic process to physiotherapists [7-9]. This is complemented with behavioural changing techniques such as motivational interviewing and shared decision-making, which are a valuable addition to usual physiotherapy[10]. By effectively using the context of the patient and focusing on strengths and the potential to adapt instead of the disease and the weaknesses, a high level of adherence to physical activity is expected to maintain. In a previous trial (CMO registration number: 2012/233), we demonstrated that the Coach2Move approach is superior to regular physiotherapy in terms of increasing physical activity, reducing frailty, improving quality of life and reducing healthcare costs [11]. In short, in less physiotherapeutic sessions, better outcomes were realized. It is therefore that the RIVM (Rijksinstituut voor Volksgezondheid en Milieu) has appraised the Coach2Move approach as good evidence for effectiveness.

Despite these promising findings, we still have questions regarding the generalisability of these findings. Our reservations towards the generalisability of the approach are caused by the following:

1. We included a modest (n=130), yet somewhat selective study sample: nearly half of the eligible individuals declined randomisation and thereby participation. We need to understand how this group of eligible non volunteers respond to Coach2Move. Therefore, we will use a study design that avoids randomisation at the patient level.
2. The Coach2Move approach significantly increased the level of moderate physical activity among the treatment group and reduced levels of frailty significantly after 6 months, but the clinical importance of these findings is still unclear. Thus, we need a replication of the effects in the light of physical functioning, a larger more variable study population and a longer follow-up.

In addition, the results from the earlier carried out RCT concerning the cost-effectiveness of Coach2Move have to be replicated on a larger scale.

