For the reasons mentioned above, it is important to further implement Coach2Move and study its effect, costs, and feasibility in current practice. A stepped wedge cluster randomised trial design is chosen because we believe that the implementation strategy will do more good than harm (making a parallel design, in which certain practices do not receive the intervention or to withdraw the intervention as would occur in a cross-over design, is unethical) and it furthermore minimizes contamination.

To further improve the implementation of Coach2Move, process evaluation will be carried out by having several meetings in which both participants and PT(G)'s will be interviewed on their experiences and their opinions on Coach2Move. Data received by process evaluation will be analysed both quantitatively and qualitatively.

The objective of this study is to assess the cost-effectiveness of the implementation of a patient and context focused tailored coaching intervention (Coach2Move) in the daily physiotherapy practice for older adults with mobility problems compared to usual physiotherapy. Our hypothesis is that Coach2Move leads to better physical outcomes and lower costs than usual care.

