3. OBJECTIVES

Primary Objective:

The aim of this study is to investigate the (cost)effectiveness of the implementation of Coach2Move physiotherapy of the management of community-dwelling older adults (≥ 70 years) with mobility problems and/or physically inactive lifestyles in a pragmatic real-world setting.

Our main research question is:

Can we improve cost-effectiveness of physiotherapy care for older adults with mobility limitations? In other words, does the implementation of the Coach2Move strategy lead to better outcomes and lower costs than usual care physiotherapy?

Secondary Objective(s):

By use of a process evaluation [12], we also aim to investigate the processes through which the Coach2Move intervention operates on outcomes and how the implementation of the program is achieved in the context of potential organisational and other differences between places and therapists.

Our secondary research questions are:

1. Which factors in the delivery procedures influence the reach of the intervention?
2. Which factors in the fidelity of the intervention influence the outcomes?
3. What are the patient experiences concerning effectiveness, pros and con's of the Coach2Move intervention?
4. What are the experiences of Physical Therapists (PT's) and Physical Therapists in Geriatrics (PTG's) concerning effectiveness and feasibility and which barriers and facilitators for implementation are perceived?
5. What are the experiences of relevant stakeholders in the multidisciplinary network concerning effectiveness and practicability of Coach2Move?

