The TUG is a measurement for functional mobility. The TUG is a test commonly used in PT(G) care and allows international comparison. During the test, the patient is instructed to rise out of a chair, walk 4 meters, turn, walk back and sit down on the chair. This procedure is timed. The average time in seconds this takes is the score on this test. Due to limitations of place in housing of patients, the test we use is slightly modified: patients are required to walk 3 meter instead of the usual 4. Outcome is the amount of time in seconds it takes to complete this test. Gait speed has shown to be a reliable proxy indicator for the physical condition of older adults [26].

Another aspect of this study is the investigation of the potential efficiency of the Coach2Move strategy compared to usual care physiotherapy in frail elderly patients referred to physiotherapy by a physician or patients that enter the physiotherapy practice by direct access. The study perspective is societal. The informal caregiver is included in this economic evaluation. The economic evaluation is based on the general principles of a cost-utility analysis.

Primary outcome measures for the economic evaluation, considering the 12 months follow-up period are costs and direct and indirect and QALYs (EQ-5D, derived from the EuroQoL). The incremental cost-effectiveness ratio (ICER) “cost per QALY gained” will be computed and uncertainty surrounding this ICER will be determined using a non parametric bootstrap method. A cost-effectiveness acceptability curve will be derived that is able to evaluate efficiency by using different thresholds (Willingness to Pay) for a QALY gained. The impact of uncertainty surrounding deterministic parameters on the ICER will be explored using one-way sensitivity analyses on the range of extremes.

The cost analysis measures on patient level, volumes of care (consisting of the production factors: personnel, materials and capacity in a prospective way using patient/caregiver based diaries and therapist scoring sheets [CRFs]). Per arm full cost prices will be determined using

real costs of participating practices. If not available, standard cost prices according to the Dutch guidelines for costing research will be used.

Certain procedures standard cost prices are not available real cost prices will be determined using activity based costing. This approach applies to the health care production part of the economic evaluation.

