9. STATISTICAL ANALYSIS

Descriptive statistics (mean, SD, proportions) will be used to report patient and PT(G) characteristics. Results on pre-structured questions on the interviews will be analysed using descriptive statistics (mean, SD, proportions).

The scores on the quality indicators of the patient files will be summarized using descriptive statistics. Descriptive summaries and charts will be produced presenting the quantitative results of the process analysis to help identify patterns of potential incomplete delivery.

a. Primary study parameter(s)

Cost-Effectiveness Analysis (CEA):

The Incremental cost-effectiveness ratio (ICER) “cost per Quality-Adjusted Life Year (QALY) gained” based on EQ-5D utilities will be computed and uncertainty will be determined using an appropriate method such as: the bootstrap method, Taylor expansion or the Fieller confidence interval method. A cost-effectiveness acceptability curve will be derived that is able to evaluate efficiency by using different thresholds (Willingness to Pay) for a QALY.

The cost analysis exists of two main parts. The direct costs of the regular physiotherapy and Coach2Move intervention will be determined on a per patient basis. Further, on patient level, volumes of care will be measured prospectively using medical records and cost questionnaires. Also travel time to the therapeutic sessions and related costs patients make will be considered.

The second part of the cost analysis consists of determining the cost prices for each volume of consumption in order to use these for multiplying the volumes registered for each participating patient. The Dutch manual for costing in evaluation analyses will be used [29]. For units of care/resources where no guideline or standard prices are available real cost prices will be determined. Research has shown that QALY's can be determined by applying a scoring method, such as developed by Versteegh and colleagues, on a meaningful health state classification measure, such as the EQ-5D. By means of the Dutch tariff, valuations can be determined for all possible health states as measured by the EQ-5D [27].

b. Secondary study parameter(s)

Quantitative Data Analysis

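### The headline economic result is a cost-per-QALY ratio with an open choice of interval; under the expected result the ratio is negative and cannot be read alone, and no interval is specified for net benefit, total cost or QALYs

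*Combined protocol and SAP*

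**What the plan says.** The Summary (Section 1) puts the ratio first among the primary outcomes: "The primary outcome measures are the cost per quality-adjusted life year (QALY) gained". Section 8.a.1 defines the components, "Primary outcome measures for the economic evaluation, considering the 12 months follow-up period are costs and direct and indirect and QALYs", takes a societal perspective, and says that "uncertainty surrounding this ICER will be determined using a non parametric bootstrap method".

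Section 9.a returns to the ratio but leaves the method open: "uncertainty will be determined using an appropriate method such as: the bootstrap method, Taylor expansion or the Fieller confidence interval method". It also plans a decision summary: "A cost-effectiveness acceptability curve will be derived that is able to evaluate efficiency by using different thresholds (Willingness to Pay) for a QALY". Section 8.a.1 plans the same curve. Neither section gives threshold values.

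On direction, Section 3 asks "does the implementation of the Coach2Move strategy lead to better outcomes and lower costs than usual care physiotherapy", and Section 2 states: "Our hypothesis is that Coach2Move leads to better physical outcomes and lower costs than usual care". Section 2 also credits the earlier trial of the intervention with "improving quality of life and reducing healthcare costs".

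Neither section mentions net monetary benefit, gives a rule for a negative ratio, or specifies a confidence interval for the difference in total societal cost or in QALYs. The multilevel model with time as a fixed effect is in Section 9.b. Section 9.a does not refer to it.

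**The concern.** There are two linked problems.

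First, Sections 8.a.1 and 9.a disagree on how uncertainty in a primary outcome will be expressed. As Section 9.a stands, the method could be picked once the data are in, and the candidates can give very different answers from the same data.

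Second, the summary measure does not suit the result the trial is looking for. Lower cost with a QALY gain makes the ratio negative. A negative ratio has no useful ordering, and it takes the same values when the intervention is better and cheaper as when it is worse and dearer. An interval for it inherits both defects. The report could then lead with a number that says neither how much was saved nor how much was gained.

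**Working it through.** **The plan's own precision figure.** The documents give no cost or QALY effect, SD or power. The only usable design figure is the standard error of 0.21 x SD in Section 6.d, stated for TUG and LAPAQ at an ICC of 0.10. Generalised least squares for that layout (4 sequences of 4 practices, 5 patients in each of 5 measured periods, fixed period effects, random practice intercept) gives 0.213 x SD, so it is reproduced. Carrying it over to costs and QALYs is an assumption.

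**Reading a negative ratio.** Write dC for the cost difference, dE for the QALY difference, ICER = dC/dE, and NMB = W x dE - dC. W = 20,000 is for illustration only. All values are assumed.

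| dC | dE | ICER | NMB |
|---|---|---|---|
| -1,000 | +0.05 | -20,000 | +2,000 |
| +1,000 | -0.05 | -20,000 | -2,000 |
| -1,000 | +0.10 | -10,000 | +3,000 |
| -500 | +0.05 | -10,000 | +1,500 |

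Rows 1 and 2 are opposite conclusions with one ICER. Rows 3 and 4 are a better and a worse result than row 1, and they too share one ICER. NMB ranks all four correctly.

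**One worked set of intervals.** Assume dC = -1,000, dE = 0.05, QALY SD 0.15, cost SD 5,000 and correlation -0.1.

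- Standard errors: 0.21 x 0.15 = 0.0315 and 0.21 x 5,000 = 1,050. Covariance: -0.1 x 0.0315 x 1,050 = -3.3075.
- Taylor: relative variance = (0.0315/0.05)² + (1,050/1,000)² - 2 x (-3.3075)/(-50) = 0.3969 + 1.1025 - 0.1323 = 1.3671. SE = 20,000 x √1.3671 = 23,385. The interval is -20,000 ± 1.96 x 23,385, or -65,834 to 25,834. It is finite and looks orderly.
- Fieller: the leading coefficient is 0.05² - 1.96² x 0.0315² = -0.0013, which is negative because dE/SE = 1.59 is below 1.96. The discriminant is also negative, so the 95% set is the whole real line.
- Bootstrap of the ratio: the sampling distribution puts 78.7% in the dominant quadrant, 15.7% in dearer-and-better, 4.3% in cheaper-and-worse and 1.3% in dominated. Percentiles of the ratio mix all four, so they share the problem.
- NMB: variance = (20,000 x 0.0315)² + 1,050² - 2 x 20,000 x (-3.3075) = 396,900 + 1,102,500 + 132,300 = 1,631,700, SE 1,277. The estimate is 2,000 (-504 to 4,504).
- Separate differences: cost -1,000 ± 1.96 x 1,050, or -3,058 to 1,058; QALY 0.05 ± 1.96 x 0.0315, or -0.012 to 0.112.

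Over 12 such settings (dE 0.02, 0.05 or 0.10; QALY SD from 0.10 to 0.25 paired with cost SD from 3,000 to 12,000), the Fieller set was the whole line in 8.

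**Repeated trials.** Assume dC = -1,000, cost SD 8,000 (SE 1,680), QALY SD 0.15-0.25 (SE 0.0315-0.0525), dE 0.01-0.08 and no correlation, with at least 200,000 simulated trials per setting.

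| Quantity | Range over settings |
|---|---|
| Estimated ICER negative | 53-72% |
| Of all trials, estimates show dominated | 0.1-12% |
| Both differences negative | 0.4-31% |
| Fieller set unbounded | 28-95% |
| Coverage of nominal 95% Taylor interval | 62-99% |
| Coverage of 95% interval for NMB | 95% |

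**Clustering and period.** An unadjusted comparison of 200 with 200 independent patients has SE = √(1/200 + 1/200) x SD = 0.10 x SD, against 0.21 x SD for the design. A bootstrap of individual patients that ignored practice and period could therefore give intervals about half as wide as they should be, whichever summary is used.

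**The case against.** The strongest reply is that the plan does not rest on the ratio alone. At each threshold the acceptability curve is the probability that net benefit is above zero. It has no sign problem, and at a threshold of zero it gives the probability of lower cost. That stands. A reader might infer that the planned economic analysis could support no conclusion, or that nothing in it addresses lower costs. The documents do not support either reading. Section 8.a.1 names costs and QALYs as primary economic outcomes, the Summary lists EQ-5D and health care utilization costs as secondary outcomes, and Section 9.b compares outcomes between groups by multilevel regression. The gap is narrower: the curve gives probabilities without an effect size, and no interval is specified for total societal cost, QALYs or net benefit.

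Four further points have force.

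- The list in Section 9.a is introduced as examples, so it is not a closed menu, and Section 8.a.1 has already named the bootstrap.
- A reader might blame Taylor and Fieller alone. An unbounded Fieller set honestly reports that the ratio is poorly determined, and a percentile bootstrap of the ratio also fails across quadrants. Deleting two methods is not enough.
- The hypothesis in Section 2 concerns physical outcomes. A QALY gain is an inference from the wider question in Section 3 and the quality-of-life finding quoted from the earlier trial. It is reasonable, but it is not stated.
- A negative ratio is ambiguous only when shown alone, since the signs of its two parts identify the quadrant. The plan does not require those signs to be reported.

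**Conclusion.** The point holds in this limited form and should be corrected. Sections 8.a.1 and 9.a conflict on the interval method. In the result the trial expects, the ratio and any interval for it cannot be interpreted alone. The acceptability curve keeps the decision analysis usable, so this is a defect in the headline estimate and not a failure of the economic evaluation.

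The sign and ordering problem is arithmetic and needs no outside figure. The percentages are illustrative: cost and QALY SDs, effects and correlation are assumed, and 0.21 x SD is stated for TUG and LAPAQ. They should not be taken as predictions for this trial. They show that, at roughly this precision, the permitted methods can differ greatly and a Taylor interval can mislead.

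**What to change.** Amend Sections 8.a.1 and 9.a so that they agree:

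1. Name the bootstrap in both and remove Taylor and Fieller. State that the bootstrap, or a model used in its place, respects practice clustering and period, as the effectiveness model in Section 9.b does.
2. Report the incremental societal cost and the incremental QALYs over 12 months, each with a 95% CI. The first addresses the lower-costs half of the question in Section 3.
3. Report incremental net monetary benefit with a 95% CI over a pre-stated willingness-to-pay grid with one reference value, alongside the acceptability curve starting at a threshold of 0.
4. Show the ICER as a number only when both differences have the same sign, and state the quadrant. When both are negative it is a saving per QALY forgone and should be kept. Otherwise state dominant or dominated.

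The cost is SAP wording and some extra output. No new data are needed. The downside is that a reference willingness-to-pay value must be named and defended before the data are seen.

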During the follow-up period costs of informal caregivers will be estimated using a caregiver-based diary (adapted version of van den Berg et al., 2006) [27] and a questionnaire on 3 months recall basis in line with the follow-up pattern of the clinical trial [28]. The friction cost-method will be applied following the Dutch guidelines for costing research [29].

Also medical costs and travel time to health care providers and related costs that patients and caregivers make will be considered (also on the basis of a diary combined with 3 months recall). Utilities from the EQ-5D will be transformed in QALY's using the trapezium method.

a.II Secondary study parameters/endpoints

To measure the level of frailty and participation the Evaluative Frailty Index (EFIP) is used. The Frailty Index is a 50-item questionnaire on deficits in health (signs, symptoms and disabilities) in multiple domains (physical, psychological, social and general health status). This Frailty Index is based on the literature and refined in Delphi rounds. It was sensitive to change in both the pilot- and the trial study. The content validity is good, psychometric properties were be tested alongside the earlier study [30]. The score on this questionnaire is expressed as the ratio of deficits present to the total number of deficits considered.

The Global Perceived Satisfaction and Effect (GPE) score is used to measure patients' satisfaction about the intervention and the perceived effect on a 7-point Likert scale ranging from very unsatisfied to very much satisfied and very much deterioration to very much improvement, respectively [31].

The Patient Specific Complaints Scale (PSC) is commonly used in PT(G) and measures the functional status of a patient. The patient selects up to three most important mobility problems in daily life, which are the most important goals to improve. The degree of hinder is scored by the patient on a 10 point numeric scale [32]. A higher score indicates a higher level of difficulty experienced in the activity mentioned.

The quality of life is tested by usage of EQ-5D questionnaire [33]. This questionnaire consists of six questions comprising 5 domains: mobility, self care, daily activities, pain and emotions. The EQ-5D is recommended where a more concise assessment is required, particularly where a substantial change in health is expected [34].

At baseline comorbidities are registered using the Cumulative Illness Rating Scale-Geriatrics (CIRS-G) [35].

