BIA will be performed according to the guidelines. Its purpose is to estimate the financial consequences of adoption and diffusion of standard use of the Coach2Move in the Netherlands. Several scenarios will be evaluated.

The aim is to assess these consequences in the medium-long term from the various budget holders' perspectives 1) wider societal perspective; 2) the more narrow perspective of the public purse; 3) the perspective of the health insurers; 4) the perspective of the health care provider.

Considering the budget impact of the new treatment mix, we will take into account market dynamics such as estimates of uptake of the Coach2Move induced treatment mix and substitution rates of usual care. For the BIA perspectives most of the cost are collected in the CEA and complemented with resources consumed not included in the CEA (like implementation costs). Both annual resource use (in terms of volumes consumed) and cost (volumes multiplied by prices) will be presented. With regard to prices and depending on the perspectives, several scenarios will be explored: charges, passenger rates (passanten tarieven), negotiated prices (if available) and real prices (CEA) based.

Effectiveness of the ultimate treatment mix will be accounted for as potential short-term savings in health care costs. The BIA will be assessed through modelling and analysed in a probabilistic way.

Deterministic uncertainty concerning BIA input such as the perspective, pricing parameters, time horizon, uptake, etc. will be dealt with by generating the budget impact as a series of scenario analyses covering a relevant range of costs.

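### The planned cost-per-QALY result leaves out implementation costs, so it answers only one of the plan's two cost questions; an implementation-inclusive ICER and acceptability curve should be pre-specified as a sensitivity analysis

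*Combined protocol and SAP*

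**What the plan says.** **What the ICER contains.** Section 9.a (CEA) says: "The direct costs of the regular physiotherapy and Coach2Move intervention will be determined on a per patient basis". Prices are then used for "multiplying the volumes registered for each participating patient". Section 8, a.1 measures volumes of care at patient level and states: "Per arm full cost prices will be determined", drawing on the practices' real costs. It also covers informal care and adds: "Also medical costs and travel time to health care providers and related costs that patients and caregivers make will be considered". The perspective is given as "The study perspective is societal". One-way sensitivity analyses on the ICER are planned there, but no implementation-cost scenario is named.

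**Where implementation costs go.** Section 9.c (BIA) says that most BIA costs are collected in the CEA, "complemented with resources consumed not included in the CEA (like implementation costs". The BIA is planned from several perspectives, including a societal one.

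**What is asked.** Section 2 sets out to "assess the cost-effectiveness of the implementation of a patient and context focused tailored coaching intervention". The main research question in section 3 is: "does the implementation of the Coach2Move strategy lead to better outcomes and lower costs than usual care physiotherapy". The hypothesis in the Summary is also about implementing Coach2Move. Section 4 and the economic part of section 8, a.1 instead word the aim as the cost-effectiveness or efficiency of Coach2Move against usual care, without reference to implementation.

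**The concern.** Section 4 defines the intervention condition by the therapists' education: patients treated after it form the intervention group. Section 7.a lists that additional education among the contrasts with usual care. The QALY side of the ratio therefore includes whatever the education achieves, while the cost side leaves out what the education uses up.

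The Summary lists cost per QALY among the primary outcomes, and lower cost is part of the hypothesis. If the ICER is read as the answer to the question in sections 2 and 3, it favours Coach2Move by the implementation cost per patient. The BIA shows that cost but produces no cost per QALY and no acceptability curve, so it cannot correct the ratio.

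**Working it through.** **Step 1: is training costed anywhere in the CEA?** The listed items are per-patient treatment costs, patient-level volumes of care, patient and caregiver travel and related costs, and informal care. Hours spent by a therapist on a course or in a peer meeting are not a volume registered for a patient. Some terms in section 8, a.1 are looser: personnel, materials and capacity as production factors, full cost prices per arm, and activity-based costing. They could absorb some overhead, but none names training, and section 9.c states directly that implementation costs are outside the CEA.

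**Step 2: effect on the result.** Let c be the implementation cost per Coach2Move patient, ΔC the delivery-only incremental cost and ΔQ the incremental QALYs.

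- Inclusive incremental cost = ΔC + c, with ΔQ unchanged.
- Net benefit at willingness to pay λ = λΔQ − ΔC − c, so it falls by c at every λ.
- If ΔQ > 0, the ICER rises by c/ΔQ. If Coach2Move saves money, the saving shrinks by c.

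Since c > 0, the direction is certain.

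**Step 3: the trial denominator.** In Figure 1 of section 4 the intervention cells number 4 + 3 + 2 + 1 = 10 and the control cells 1 + 2 + 3 + 4 = 10. With 4 practices per group and 5 patients per practice-period (section 6.d), each condition has 10 × 4 × 5 = 200 patients. This reproduces the 200 + 200 = 400 of sections 4 and 6.d.

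**Step 4: therapists.** The Summary has at least two therapists trained in each of 16 practices, so at least 2 × 16 = 32.

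**Step 5: hours per therapist (H).** The documents give no session lengths. Assumed: day part 4 h, day 8 h, peer meeting 2 to 3 h, e-learning 0 h extra (counted inside the course) to 4 h.

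- Low (two day parts, two meetings): 2×4 + 2×2 + 0 = 12 h.
- High (two days, three meetings): 2×8 + 3×3 + 4 = 29 h.
- Ratio: 29/12 = 2.4, due partly to the conflicting training descriptions.

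**Step 6: hours per patient.** This is H/n, where n is the number of Coach2Move patients per therapist over the allocation horizon. Trial-only allocation at 32 therapists gives n = 200/32 = 6.25. The other values of n are assumed.

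| n | H = 12 | H = 29 |
|---|---|---|
| 6.25 (trial only) | 1.92 | 4.64 |
| 25 | 0.48 | 1.16 |
| 50 | 0.24 | 0.58 |
| 100 | 0.12 | 0.29 |
| 200 | 0.06 | 0.145 |

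The trial-only row rests on the minimum number of therapists. With an assumed three per practice (48), it becomes 12×48/200 = 2.88 to 29×48/200 = 6.96 h. Across the rows of the table, n varies 200/6.25 = 32-fold; that span reflects the choice of 200 as the upper end.

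**Step 7: a benchmark from the documents.** Section 7.a gives a 60-minute Coach2Move intake against 30 minutes conventionally. That is 0.5 h more per patient, and as delivery time it falls within the CEA. The implementation time is of the same order at n = 25 to 50 and well below it at n = 200.

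The hours are not converted to euros or to an ICER shift, because the documents give no hourly price, QALY gain or standard error of net benefit. Trainer, supervision and ICT costs are not counted.

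**The case against.** The strongest reply is that a delivery-only CEA with roll-out costs in the BIA is a legitimate and disclosed choice. Sections 4 and 8 word the aim as the efficiency of Coach2Move itself, and the planned ICER answers that. It also suits a steady-state comparison: no measurements are taken during implementation and wash-out, so the learning phase is outside the effect estimate too. This stands, and it is why the planned ICER should be kept.

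A reader might infer that the plan ignores implementation costs or has no output that reflects them. The documents do not support that. The BIA includes these costs, takes a societal perspective among others, allows for substitution of usual care and short-term savings, and varies uptake and time horizon by scenario. It therefore addresses the lower-costs half of the question in section 3. Only cost per QALY and the acceptability curve with implementation included are missing.

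The size may also be small. Over long horizons the hours per patient are a fraction of the extra intake time, and the amount could be added later if hours are logged. Trial success in section 8, a.1 is declared on LAPAQ and TUG alone. All this limits the weight of the point, but it does not remove the mismatch between the ICER and the question in sections 2 and 3.

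**Conclusion.** The point holds in a limited form. The exclusion is explicit and nothing in the costing text reverses it. For the question worded around implementation, the planned incremental cost is too low by the per-patient implementation cost, in favour of Coach2Move. For the question worded around Coach2Move itself, the planned ICER is adequate.

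Only the direction follows from the documents. The size depends on the allocation horizon, the number of therapists trained (at least 32) and the training hours. The figures of 0.06 to 4.64 h per patient rest on assumed session lengths, assumed patient numbers beyond the trial and that minimum number of therapists.

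A reader might go further and infer that inclusion would reverse a finding of lower costs or move the acceptability curve substantially. The documents do not support that: without prices, an expected saving or a standard error of net benefit, neither claim can be tested. Charging everything to trial patients is also an extreme allocation, because trained therapists use the approach with other patients as well (Summary and section 8.d).

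**What to change.** Keep the delivery-only ICER. State in section 9.a that training and other implementation costs are outside it, and which wording of the objective it answers.

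Add to the one-way sensitivity analyses of section 8, a.1 a pre-specified implementation-inclusive ICER and acceptability curve. Use the implementation resources estimated for the BIA: therapist time for e-learning, course and peer meetings, plus trainer cost. Allocate them per patient over a horizon fixed before results are known, with allocation to the roughly 200 trial intervention patients as the extreme scenario.

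Reconcile the training descriptions so that the hours can be costed:

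- two day parts in the Summary's implementation paragraph, against two days in its intervention paragraph and in sections 4 and 7.b;
- two peer meetings in one part of section 7.b, against three in the Summary, section 4 and later in 7.b;
- e-learning before the course in the Summary, against e-learning as part of the education in 7.b.

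The cost is a log of training and meeting hours per therapist, one more cost line, one extra ICER and curve, and a judgement on the horizon. No further patient data are needed. The second ICER will be somewhat less favourable to Coach2Move.
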